7.2.2 Serious adverse events (SAEs)

A serious adverse event is any untoward medical occurrence or effect that:

- Results in death;
- Is life threatening (at the time of the event);
- Requires hospitalisation or prolongation of existing inpatients' hospitalisation;

- Admissions due to relapse episode mania or depression (part of routine care)
- Results in persistent or significant disability or incapacity;
- Is a congenital anomaly or birth defect; or
- Any other important medical event that did not result in any of the outcomes listed above due to medical or surgical intervention but could have been based upon appropriate judgement by the investigator.

The investigator will report all SAEs to the sponsor without undue delay after obtaining knowledge of the events, except for the following SAEs:

- Relapse episode mania or depression as relapse is one of the secondary objectives of this study.

The sponsor will report the SAEs through the web portal *ToetsingOnline* to the accredited METC that approved the protocol, within 7 days of first knowledge for SAEs that result in death or are life threatening followed by a period of maximum of 8 days to complete the initial preliminary report. All other SAEs will be reported within a period of maximum 15 days after the sponsor has first knowledge of the serious adverse events.

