- Level of anxiety, using the Beck Anxiety Inventory (BAI) (Osman, Barrios, Aukes, Osman, & Markway, 1993). The BAI is a 21-item self-report questionnaire used for measuring the severity of anxiety. Answers are rated on a 4-point Likert scale (0-3). This is administered weekly throughout the duration of the study.
- Level of general functioning and coping: Participants rate their level of functioning using the Longitudinal Interval Follow up Evaluation – Range of Impaired Functioning Tool (Leon et al., 1999). This is a brief scale for people suffering from affective disorders, measuring four different functional areas (employment, interpersonal relations, satisfaction and recreation) on a 5-point Likert scale (low rating implies higher functioning). This is administered at T0, T1, T2, T3 and T4.
- Level of hopelessness: participants rate their hopelessness using the Beck Hopelessness Scale (Beck, Brown, & Steer, 1997), The BHS is a 20 item self-report scale measuring three aspects of hopelessness: feelings about the future, motivation and expectations. The BHS demonstrates good internal consistency (alpha = .93) and has high reliability in psychiatric samples (Beck et al., 1997). The BHS is administered at T0, T1, T2, T3 and T4.
- To assess number of relapses into mania and depression, scores on the above measures (ASRM for mania and QIDS-SR for depression) are used. Scores on the ASRM of 5 or more indicate a relapse into mania, a score of 10 or more on the QIDS a relapse into depression. This is measured using the weekly scores on the ASRM and QIDS-SR during the weekly measures in the follow up period (until 16 weeks after the end of either ImCT or psychoeducation).

To assess if (4) problematic imagery the following measures will be used:

- The Visual Analogue Scales of Imagery Characteristics (VAS-Imagery) have been tailored to BD populations. The scales range from 0-9. Examples are "How real / vivid / absorbing / preoccupying / compelling have your image(s) been over the past week"; "To which extent could you understand the role that the image(s) play in your mood instability?"; "To which extent could you find positive / helpful way of using the image(s)?" Target imagery is measured weekly throughout the duration of the study. Imagery characteristics are measured weekly throughout the duration of the study in both ImCT and psychoeducation treatment conditions.

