6.4.1 Specific criteria for withdrawal (if applicable)

If patients experience relapse (mania or depression) and require a hospital admission for longer than one week, they will be excluded from this trial.

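### Relapse is exempted from SAE reporting because it is an endpoint, but the relapse endpoint does not reliably capture relapse admissions, so an admission can miss both the SAE report and the comparison

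*Combined protocol and SAP*

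**What the plan says.** **SAE definition (7.2.2).** A relapse admission qualifies twice: under the general criterion "Requires hospitalisation or prolongation of existing inpatients' hospitalisation", and under its own bullet, "Admissions due to relapse episode mania or depression (part of routine care".

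**Exemption (7.2.2).** The same section continues: "The investigator will report all SAEs to the sponsor without undue delay after obtaining knowledge of the events, except for the following SAEs". The single exception is "Relapse episode mania or depression as relapse is one of the secondary objectives of this study". The wording refers to an episode. It neither includes nor carves out the admissions listed just above it.

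**Relapse endpoint (6.1.2).** "Scores on the ASRM of 5 or more indicate a relapse into mania, a score of 10 or more on the QIDS a relapse into" (the sentence ends with depression). On timing: "This is measured using the weekly scores on the ASRM and QIDS-SR during the weekly measures in the follow up period", which runs to 16 weeks after treatment ends. Section 8 repeats the cut-offs and the follow-up window and compares the arms by chi-square. Admission is not a component in either place.

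**Longer admissions (6.4.1).** "If patients experience relapse (mania or depression) and require a hospital admission for longer than one week, they will be excluded from this trial". Section 6.6 then describes only usual care for withdrawn patients.

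**Analysis set (section 8).** Outcomes other than the primary are used only where pre- and post-measures are complete, yet intention-to-treat is named as the central analysis.

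**Oversight.** There is no DSMB (7.4), and 10.2 says no monitoring plan is needed.

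**The concern.** Exempting an event from SAE reporting because it is an endpoint makes sense only if the endpoint captures the event. Here the two are defined differently: the SAE list refers to admissions at any time in the study, while the endpoint refers to self-report scores in one part of it.

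Two things are at stake. The sponsor's reporting deadlines to the ethics committee in 7.2.2 run from the sponsor's own knowledge of the event, and the exemption removes the investigator's stated duty to supply it. In addition, the most severe relapses may drop out of the between-arm relapse comparison, which is one of the trial's secondary objectives. An imbalance in admissions between the arms could then go untabulated in a trial without a DSMB.

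**Working it through.** The plan gives no figure for this point, so the check compares the sections and then sizes the gap.

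**1. Weeks covered by the endpoint.** Inputs from sections 3 and 6.3.2: baseline 4 weeks; treatment 12 (ImCT) or 6 (psychoeducation); follow-up 16.
- Total: 4 + 12 + 16 = 32 and 4 + 6 + 16 = 26 weeks. Both agree with section 3.
- After allocation: 12 + 16 = 28 and 6 + 16 = 22 weeks.
- After allocation but outside the endpoint: 12/28 = 43% and 6/22 = 27%.

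The uncounted period after allocation is twice as long in the ImCT arm.

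**2. What happens to an admission, by timing and length.**
- *During treatment, any length:* it cannot enter the endpoint. If it lasts more than a week the patient is also excluded under 6.4.1, has no described follow-up scores, and would normally lack the post-intervention measure that section 8 requires.
- *During follow-up, more than a week:* it counts only if a weekly score reached a cut-off before measurement stopped. If the post-measure means T2, such a patient passes the completeness rule, but the later weeks are unobserved.
- *During follow-up, a week or less:* the patient stays in, and any weekly score at or above a cut-off counts.

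In all three cases, whether the investigator reports the admission to the sponsor depends on how the exemption is read.

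**3. Intention-to-treat.** Dropping patients excluded under 6.4.1, or those failing the completeness rule, is not compatible with intention-to-treat as the central analysis. Section 8 does not say which rule prevails for relapse.

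**4. Size of the uncounted part.** Section 1 cites 60% relapse within two years (104 weeks). *Assumption:* constant hazard, equal in both arms, so the risk over w weeks is 1 − 0.4^(w/104). With 48 patients per arm (4.4):
- ImCT, 12 weeks: 1 − 0.4^(12/104) = 10.0%; 48 × 0.100 = 4.8.
- Psychoeducation, 6 weeks: 1 − 0.4^(6/104) = 5.1%; 48 × 0.051 = 2.5.
- Together: about 7.3 relapses in treatment weeks.

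The share of relapses that lead to admission is not in the documents. Illustrative shares: 0% gives 0 admissions, 25% gives 1.8, 50% gives 3.6, 100% gives 7.3.

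**5. Why raw counts would mislead.** The 4.8 against 2.5 arises with identical hazards, purely from treatment length. With full retention the treatment periods hold 48 × 12 = 576 and 48 × 6 = 288 person-weeks.

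**The case against.** The case on the other side is substantial, and much of it stands.

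- **A reader might infer that severe relapses disappear from every record.** They do not. The exemption concerns reporting to the sponsor, not recording. Section 7.2.1 has all reported or observed adverse events recorded, with no exception for relapse, and 7.3 follows them up. Sections 10.2 and 10.4 put serious adverse events in the annual summary to the ethics committee without repeating the exemption. An admission of more than a week also shows as an exclusion.
- **A reader might infer that every relapse admission is exempt.** The text does not settle this. If the exemption covers only the episode and not the admission, admissions are reported and the safety half of the concern largely falls away. The ambiguity remains a fault, since staff could handle identical admissions differently.
- **A reader might infer that the termination rule in 6.7 is left without information.** That rule refers to drop-out and deterioration and does not name SAE reports as its source. Exclusions are visible as drop-out. Weekly scores and the daily life chart run through treatment, and the chart's extreme ratings are worded in terms of needing admission (6.1.1). However, no relapse analysis uses these treatment-period data.
- **A reader might size the problem at about 19 relapses**, from 48 × 21.9% over 28 weeks plus 48 × 17.6% over 22 weeks. That counts all relapses after allocation, including follow-up weeks in which the endpoint can count them.
- **The follow-up window is deliberate.** It matches the relapse hypothesis in section 2 and gives both arms the same 16 weeks. That is a good reason to keep the window, but it does not make the endpoint a substitute for SAE reports during treatment.
- **Relapse is expected in this condition (7.4).** That explains individual events. It does not address a difference between arms.

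**Conclusion.** The concern holds in a limited form. Section 7.2.2 leaves the status of a relapse admission unclear, and its reason for the exemption does not hold for admissions during treatment, or for follow-up admissions without a qualifying weekly score. If the exemption is read to include admissions, such an event is neither reported to the sponsor as an SAE nor counted as a relapse. It then survives in the site adverse event record, the exclusion count and possibly the annual summary, with no stated comparison by arm. The conflict between the 6.4.1 exclusion, the completeness rule and intention-to-treat does not depend on how the exemption is read.

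The uncounted treatment weeks would hold about 7 relapses, of which anywhere from none to all might be admissions. This rests on the cited 60% (whose definition of relapse the documents do not give), a constant hazard equal in both arms, and 48 patients per arm. The documents do not allow the direction or size of any bias in the relapse comparison to be stated. The point should be corrected, but it does not touch the primary outcome.

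**What to change.** 1. Reconcile 7.2.2 with 6.1.2 and 6.4.1 so that the status of a relapse admission, as SAE, as reportable event and as endpoint event, is unambiguous. Which reporting route applies is for the sponsor and the ethics committee to settle.
2. Whatever the route, record every relapse admission from allocation onward, with dates.
3. Count an admission during the 16-week follow-up as a relapse event in the secondary analysis, alongside the score cut-offs.
4. Keep patients excluded under 6.4.1 in the intention-to-treat relapse analysis. State in advance how follow-up relapse status is assigned when weekly scores have stopped, and say that the completeness rule in section 8 does not remove these patients.
5. Tabulate treatment-period admissions and 6.4.1 exclusions by arm, per person-week. Do not add treatment-period admissions to the endpoint itself, which would then compare 28 weeks at risk with 22.

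The cost is protocol and SAP wording, one CRF item and a little more reporting work. Withdrawn patients remain in care at the same centre (6.6), so the admission information should be within reach.

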7.3 Follow-up of adverse events

All AEs will be followed until they have abated, or until a stable situation has been reached. Depending on the event, follow up may require additional tests or medical procedures as indicated, and/or referral to the general physician or a medical specialist. SAEs need to be reported till end of study within the Netherlands, as defined in the protocol

7.4 [Data Safety Monitoring Board (DSMB) / Safety Committee]

In this study a DSMB is not needed, as the interventions consists of either care as usual, or a variation on care as usual. Relapse episodes (mania or depression) are expected as part of the condition. Appropriate care for this is in place and considered care as usual.

8. STATISTICAL ANALYSIS

First, descriptive analyses will be used to establish mean scores, standard deviations and to identify outliers. Missing data from our primary outcome variable, will be listwise deleted. In our other outcome variables, data will only be included if pre- and post-measures are completed.

Second, the data will be checked with respect to violation of assumptions (such as error independency, non-normal distributions) for variance-based models.

Primary outcome variable: mood variability:

To assess if there is a stronger decrease in mood variability in the ImCT intervention condition as compared to the psychoeducation condition, multivariate repeated measures analyses are applied. Dependent variables are the scores on the ALS-18 (baseline, T0; pre-treatment, T1; post-treatment, T2; 8-weeks follow-up, T3; 16-weeks follow-up, T4) with treatment condition (ImCT, psychoeducation) as between subjects variable.

In addition, to assess reductions in mood variability during the interventions (ImCT, psychoeducation) compared to mood variability during the baseline period, daily mood measures with the National Institute of Mental Health Life Chart Methodology (NIMH-LCM) Prospective Self-Rating of mood (both mania and depression) are assessed, using a case series design, where participants baseline ratings can act as their own control (Arntz, Sofi, & van Breukelen, 2013). Changes in mood variability are investigated using sequence analysis with R-software (package TraMineR version 1.8-10); (Gabadinho, Ritschard, Muller, & Studer, 2011) on the daily scores. Sequences consist of a series of subsequent states (daily scores) and similarities between sequences are calculated with the Optimal Matching technique (OM). Sequences will be defined as day scores from 28 days prior to starting the interventions, until 112 days after the end of interventions. Rather homogenous groups of trajectories (clusters) will be derived from the distance matrix that result from the OM technique. To this end, cluster analysis will be applied. Shannon entropy of transversal state of the scores on each day will be calculated and plotted (Gabadinho et al., 2011). Entropy is a measure of diversity of states (a measure of mood variability) within sequences and varies between zero (all sequences in the same state) to 1 (maximum diversity). To explore the relationship between diversity in states (mood variability) and background characteristics, this longitudinal entropy will be regressed on co-variates (gender, medication). Also, sequences of scores at the start of treatment will be compared to subsequences during treatment and during the follow-up period to explore change over time.

Secondary outcome variables: depression, anxiety, mania, general functioning and coping, hopelessness, number of relapses into mania or depression, and changes in imagery:

To assess if (2a) level of depression, mania and anxiety, (2b) general functioning and coping, and hopelessness increase/decline more in the ImCT intervention compared to psychoeducation treatment two types of multivariate repeated measures analyses are applied, both with treatment condition (ImCT, psychoeducation treatment) as independent, between groups variable. In the first type of analyses, the dependent variables are the scores of the weekly measures for depression, anxiety and mania (QIDS-SR, BAI, ASRM). In the second type of analyses, time (T0, T1, T2, T3 and T4) is used as within between subject variables and scores of the same instruments and general functioning and coping and hopelessness (ALS-18, IFE-RIFT, BHS) are used as dependent variables.

To assess if (3) number of relapse into mania or depression decline more in the ImCT intervention compared to psychoeducation treatment Chi-square analyses are applied with as dependent variable number of relapses into mania or depression, using cut-of scores on the ASRM and QIDS-SR during the follow-up period and treatment condition (ImCT, psychoeducation treatment) as between groups variable.

To assess if (4) problematic imagery decreases and imagery characteristics changes more by using the ImCT intervention compared to psychoeducation treatment, comparable to 2a and 2b, two types of multivariate repeated measures analyses are applied, both with treatment condition (ImCT, psychoeducation treatment) as between groups variable. In the first type of analyses, the dependent variables are the scores of the weekly measures of imagery (VAS). In the second type of analyses, time (T0, T1, T2, T3 and T4) is used as within between subject variables and scores of imagery (MICQ-BD and DIS) are used as dependent variables.

Where possible multivariate analyses are used to analyse differences between groups, and repeated-measures ANOVA to analyse difference within groups. These will be used to minimise the correlations and dependencies between variables. In order to allow for reliable multivariate analysis, assumptions of sphericity are tested. Multivariate analyses between groups (ImCT, psychoeducation treatment) and repeated-measures ANOVA within groups (T0, T1, T2, T3, T4) are used to determine an omnibus effect. If differences are significant, post hoc analyses (mostly independent T-test) will be used to determine individual differences between groups and between points in time. Bonferoni corrections are used to correct for multiple testing.

Intention-to-treat analyses will constitute the central analyses and completers analyses will be done as supplementary analyses.

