2. OBJECTIVES

Primary Objective and secondary objectives:

The present research project elaborates on a pilot study by Holmes and colleagues (2016) and an audit (Hales et al., 2018) using a new cognitive behavioural therapy enhanced with imagery techniques (ImCT), with an aim to improve the effectiveness of CBT for patients suffering from bipolar disorder. The pilot study (Holmes et al., 2016) found promising treatment effects but a controlled feasibility study is needed to test whether this treatment is more effective than regular treatment. Therefore, this research projects examines the effect of this new ImCT treatment, by comparing this intervention to psychoeducation treatment, one of the most regularly applied psychological intervention for bipolar disorder. The current

study will provide new insights for an upcoming large RCT evaluating the effectiveness of ImCT in the UK.

[figure not shown]
Our primary objective is to estimate the effects of ImCT compared to psychoeducation on mood variability. We hypothesise that (1) mood variability (primary outcome variable) will show stronger decreases in BD patients receiving ImCT at end of the intervention (T2), at follow-up measurement 8 weeks after concluding the interventions (T3) and at follow-up measurement 16 weeks after concluding the interventions (T4) than psychoeducation. Additionally, the effects of both treatments separately are also compared to baseline period preceding both treatments.

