6.6 Follow-up of subjects withdrawn from treatment

If patients are withdrawn from the study, they will continue with care as usual from the specialised centre for bipolar disorders of the GGzE.

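### Listwise deletion over T0–T4 makes the central ALS-18 analysis complete-case, discards collected scores, and leaves intention-to-treat and completers undefined

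*Combined protocol and SAP*

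**What the plan says.** Section 8 (Statistical analysis) gives two rules for missing data. For the primary outcome: "Missing data from our primary outcome variable, will be listwise deleted". For the rest: "In our other outcome variables, data will only be included if pre- and post-measures are completed".

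The primary model is a multivariate repeated-measures analysis by treatment condition. "Dependent variables are the scores on the ALS-18 (baseline, T0; pre-treatment, T1; post-treatment, T2; 8-weeks follow-up, T3", and the list ends with T4 at 16 weeks. After a significant omnibus result, "post hoc analyses (mostly independent T-test) will be used to determine individual differences between groups and between points in time".

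The section closes with "Intention-to-treat analyses will constitute the central analyses and completers analyses will be done as supplementary analyses". Neither set is defined there or elsewhere. No mixed model, imputation or missing-data sensitivity analysis is described.

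Three other sections bear on this:
- Section 2 states the primary hypothesis separately for T2, T3 and T4.
- Section 6.4.1 says: "If patients experience relapse (mania or depression) and require a hospital admission for longer than one week, they will be excluded from this trial".
- Section 6.6 says only: "If patients are withdrawn from the study, they will continue with care as usual". It describes no further collection of outcomes.

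**The concern.** Listwise deletion combined with a five-wave model removes a patient entirely if any one score is absent. A patient with a valid T2 score but no T4 score drops out of the comparison at T2 as well, although the end of treatment has its own hypothesis. The result is a complete-case analysis. Even if intention-to-treat is taken to mean only analysis by allocated arm, the reader cannot tell how the central analysis differs from the completers analysis.

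Two things are at stake. One is precision, because scores already collected are thrown away. The other is bias. Under section 6.4.1 some loss is tied to relapse, and so plausibly to mood variability. If that loss differs between arms, the patients left are no longer a fair comparison. Time at risk after allocation also differs by design (section 3): 32 − 4 = 28 weeks for ImCT and 26 − 4 = 22 weeks for psychoeducation.

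**Working it through.** **Inputs from section 4.4.** d = 0.6, two-sided alpha 0.05, 80% power, 45 evaluable per arm, dropout 1 in 15, 48 randomised per arm. No per-wave rate and no between-wave correlation is given, so both are assumed below and shown as ranges.

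**1. The plan's own figure.** For a two-sample t-test with noncentrality 0.6 × √(n/2) and 2n − 2 degrees of freedom, power is 79.5% at n = 44 and 80.4% at n = 45. So 45 is reproduced. After the planned loss, 48 × 14/15 = 44.8 per arm, with power 80.2%. The sample size is not in question.

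**2. Who is left after listwise deletion.** Assume T0 and T1 are complete and a share m misses each of T2, T3 and T4 independently.

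| Per arm | m = 5% | m = 10% |
|---|---|---|
| All scores present, 48(1−m)³ | 41.2 | 35.0 |
| Deleted with at least one post-treatment score, 48[1−(1−m)³−m³] | 6.8 | 13.0 |
| Deleted although T2 is present, 48(1−m)[1−(1−m)²] | 4.4 | 8.2 |
| T2 scores collected, 48(1−m) | 45.6 | 43.2 |
| t-test power at T2, listwise | 77% | 70% |
| t-test power at T2, every T2 score | 81% | 79% |
| Ratio of T0-to-T2 standard errors, 1/(1−m) | 1.05 | 1.11 |

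If instead the same patients miss all three waves, 45.6 or 43.2 per arm remain, power is 81% or 79%, and deletion costs no further power.

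**3. The omnibus test.** This is the group-by-time multivariate test with 4 degrees of freedom, assuming arm differences of 0, 0, 0.6, 0.6 and 0.6 SD over T0–T4.

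| Correlation assumed | 44.8 per arm | 41.2 per arm | 35.0 per arm |
|---|---|---|---|
| Compound symmetry 0.5 | 95% | 92% | 87% |
| Compound symmetry 0.65 | 99% | 99% | 97% |
| AR(1) 0.5 | 69% | 64% | 56% |
| AR(1) 0.65 | 80% | 76% | 68% |
| AR(1) 0.8 | 96% | 94% | 89% |

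**4. Bias.** Suppose loss after T2 depends on the T2 score in one arm (logistic slope 1 per SD) and is random and equally large in the other. The true difference is 0.60 SD and correlations run from 0.5 to 0.8. The figures are simulated, accurate to about 0.01. The ends of each range correspond to the affected arm being one or the other.

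| Complete-case T0-to-T2 change difference | 6.7% loss | 14.3% loss |
|---|---|---|
| Compound symmetry | 0.57–0.63 | 0.54–0.66 |
| AR(1) | 0.56–0.65 | 0.50–0.70 |

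The T0-to-T4 difference stays at 0.60, because T0 and T4 are equally correlated with T2 in both structures. An estimate using all scores returns 0.60 by construction, since loss here is random given T2. The largest shift is 0.10. With a T0–T2 correlation of 0.25 (AR(1) 0.5) and 48 × (1 − 0.143) = 41.1 per arm, the standard error is √(4 × 0.75 / 41.1) = 0.27, so the shift is about 0.4 of a standard error.

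**5. Loss driven by an unseen score.** If loss depends on the unobserved T3 score (compound symmetry, 14.3% loss), the T0-to-T3 difference is 0.54–0.66 listwise and 0.52–0.68 likelihood-based. The mixed model does not repair this case.

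**6. Unequal follow-up.** With the same weekly loss rate over 28 and 22 weeks, an average loss of 6.7% splits into 7.4% and 5.9%. An average of 14.3% splits into 15.9% and 12.7%.

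**The case against.** The strongest reply is about size. The only loss rate in the documents is 1 in 15, and at that rate power is 80%. The 5% and 10% cases amount to total losses of 14% and 27%, which nothing in the plan supports. If independent misses are set to total 6.7%, about 46.9 per arm have a T2 score and power is about 82% with all of them, against 80% listwise: a cost of 2 points. Allocation follows a four-week run-in that patients must complete (sections 4.2 and 6.3.2), which also argues for low loss. All of this stands, and the figures above are illustrations.

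The documented route to loss is also one-way: exclusion, then usual care. Under that pattern no T4 score is thrown away. This reduces the cost without removing it. Patients lost after T2 or T3 still forfeit the scores they gave, and listwise standard errors remain about 1–5% larger than those of a likelihood model at T2, T3 and T4.

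The single-wave t-tests might be run on all patients present at that wave. Section 8 does not say so, and the omnibus test that precedes them would be complete-case regardless. In some rows of its power table, correlation matters more than deletion.

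A mixed model gives little help if relapse-related loss depends on unseen scores. With AR(1) correlation at 14.3% loss, T0-to-T3 is 0.49–0.70 listwise and 0.51–0.69 likelihood-based, so roughly equal. That is correct, and it is why a sensitivity analysis is needed as well. The difference in follow-up time is a minor contributor, and unequal loss alone does not create bias.

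**Conclusion.** The concern holds and should be fixed. That the central ALS-18 analysis is complete-case while labelled intention-to-treat follows from section 8 itself and needs no assumed rate. That deletion extends over all five waves is an inference from the rule and the model together, but the natural reading.

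The practical cost ranges from nothing beyond the planned loss, if the same patients miss every post-treatment wave, to about 4 or 9 points of t-test power at T2 under independent misses of 5% or 10% per wave. Bias is possible, of unknown direction and probably modest. The feasibility label does not dispose of the point: section 2 makes estimating the treatment effect the primary objective, and section 1 says retention still has to be estimated.

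**What to change.** - Define intention-to-treat as all randomised patients in their allocated arm. Define completers by sessions, assessments or both.
- Replace both deletion rules with a likelihood-based mixed model for repeated measures, or multiple imputation, using every available score. Align the model wording throughout section 8.
- Keep the complete-case analysis as supplementary.
- Add one sensitivity analysis for loss not at random, aimed at relapse-related exclusion.
- State that data collected before exclusion stay in the analysis. Reconcile sections 6.4.1 and 6.6 with section 8 on whether outcomes are collected afterwards.

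The cost is analysis-plan wording and a short protocol amendment, with no new patients or measures. The downside is a little more analysis work and a missing-at-random assumption in the main model. Relapse-related loss may break that assumption, and the mixed model alone does not answer it.
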